**Exclusion criteria:**

- 1) Alzheimer's Disease or other neurodegenerative disease such as Parkinson's Disease;
- 2) Current use or use in the past 3 months of antimicrobial or steroid drugs;
- 3) Medical conditions affecting immune status (e.g., heart failure, inflammatory bowel disease, hepatitis C, HIV);
- 4) International travel in the past 3 months.
- 5) Previous known side effect or negative reaction to VSL#3 or *Triphala*.

Note that heart failure, inflammatory bowel disease, hepatitis C, and HIV patients are excluded due to these diseases featuring variable and significantly altered immune status and gut microbiome, which are the main outcome measures of the study. This pilot study seeks to identify relatively healthy elderly subjects to assess these markers in the context of dietary supplementation.

**Assessment visits.** Assessment personnel will be naive to the participant group assignment. Testing will take place at SOM Building 4. At T1 (baseline): participants will 1) review their study responsibilities with the opportunity to reconsider participation 2) provide a stool and small blood sample for biomarker assessment; 3) complete psychosocial measurements via questionnaires; 4) receive group assignment instructions at the end of the visit. Measures will be repeated at T2 (post-intervention period).

**Randomization.** A computer-generated randomization algorithm will determine group assignment to ensure that participant demographics are evenly distributed across study conditions.

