**Experimental Conditions:**

Interested patients will provide informed consent and then be randomized to participate in the synbiotic, *Triphala* alone, or placebo alone group. Subjects will receive stool kits and a set of questionnaires to fill out at T1. Subjects will bring their morning stool sample and fill out the questionnaires again at T2.

Synbiotic Group. Subjects will be provided both written and verbal instructions and given a kit containing encapsulated Organic *Triphala* powder (Banyan Botanicals, Inc.) and VSL#3® (VSL Pharmaceuticals, Inc.) capsules. Subjects will take 2 grams of encapsulated organic *Triphala* powder and 1 capsule of VSL#3 with room temperature water in the morning and at bedtime.

Herb Only Group. Subjects will be provided both written and verbal instructions and given a kit containing encapsulated Organic *Triphala* powder (Banyan Botanicals, Inc.). Subjects will take 2 grams of organic *Triphala* powder with a few ounces of room temperature water in the morning and at bedtime.

Placebo Group. Subjects will be provided both written and verbal instructions and given a kit containing placebo capsules. Subjects will be instructed to take 2 (inert) capsules with room temperature water in the morning and at bedtime.

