*Leisure Time Exercise Questionnaire (LTEQ):* By Godin and Shephard, a valid and reliable self-administered questionnaire designed to measure an individual's regular physical activity level.

*Alcohol Use Disorders Identification Test (AUDIT):* A simple screening method to assess alcohol use.

Exploratory Outcomes Hypothesis: Psychological health.

*Beck Depression Scale (BDI)-II:* A 21-item self-report scale used to measure depression symptom changes.

*Perceived Stress Scale (PSS):* Assesses unpredictability, uncontrollability, and overwork/stress.

*Perceived Benefits Scale (PBS):* Yields subscales of enhanced self-efficacy, increased community closeness, increased compassion, increased faith, lifestyle changes, enhanced family closeness, and material gain.

*Positive and Negative Affect Schedule (PANAS):* Two 10 item scales of positive and negative emotionality.

*Satisfaction with Life Scale (SWLS):* Assesses satisfaction with life as a whole and has high internal consistency and temporal reliability.

*The Mindful Eating Questionnaire (MEQ):* Measures five constructs related to mindfulness of eating behavior:

disinhibition (inability to stop eating when full); external cues (eating in response to environmental cues); emotional eating (eating in response to emotional state); awareness (being aware and appreciative of effects of food on senses) and distraction (focus on other activities while eating) with 28 items scored on a 4 point scale - "Never/Rarely," "Sometimes," "Often," and "Usually/Always." This instrument has a good internal consistency reliability (Cronbach's alpha = 0.64), and construct validity.

**Ayurvedic Health Forms (AHF):** The Chopra Center's 102-item Mind/Body Quiz is used to assess body and mind constitution and state of imbalance in Clinical Ayurveda on a 3-point scale – "Never", "Occasionally", "Very often." The *Ojas/Ama* Quiz is a 20-item assessment of Yes/No questions to determine level of *Ojas* and *Ama*, which are Ayurvedic Medical classifications of immune strength and toxic burden.

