#### **Statistical Issues**

Analytic Approach. Summary statistics (means, SDs, ranges, frequencies) will be computed for all variables of interest and compared between the treatment arms at baseline using 2-sample tests to test if randomization achieved balance in key covariates across groups. In the event of pre-existing variable group differences associated with dependent or relevant clinical variables, the nuisance variables will be statistically controlled. Outcome measures (e.g. health-related behaviors, psychological health, and objective measures of microbiome health and inflammation) will be transformed as needed to better approximate Gaussian distributions. The proposed study period is 2 months; hence we anticipate little loss-to-follow-up. However, subjects may drop out for a variety of reasons. It is important to take missing data into account when testing hypotheses of interest. Mixed-models can be applied even if some observations are missing as long as the data are "missing at random". Missing data (e.g., drop-outs) will be tested to determine if it is informative, and the methods to test for completely random dropouts will be applied. If needed, pattern-mixture models will be developed which take "missingness" into account when estimating parameters of interest using the methods of Park & Lee.

Analysis Plan. Two sample *t*-tests will be used to compare change scores (post-treatment minus pretreatment) in each outcome. Given the multiple outcomes, we will also use O'Brien's test which can be used to compare multiple endpoints across groups; we will apply O'Brien's test to the multiple outcomes for each hypothesis (e.g., psychological health via positive and negative affect, depressive symptoms; health behaviors via diet, physical activity, medication adherence, and alcohol usage). The O'Brien test statistic is a weighted linear combination of the *t*-statistics for each outcome. Finally, we will fit mixed effects models, with a subject-specific intercept included to allow for individual variability in outcome. Main covariate effects will be treatment group, time (pre-treatment and immediately post-treatment), and the group X time interaction. Likelihood ratio tests will be used to test the significance of these covariates. A significant group X time interaction will indicate that outcome trajectories differ across treatment groups.

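### The Perceived Benefits Scale measures perceived gains, yet it is given before treatment and analysed as T2 minus T1, which makes the score hard to interpret and may cost precision

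*Combined protocol and SAP*

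**What the plan says.** Section 9, Assessment Outcomes, places the PBS under the heading "Exploratory Outcomes Hypothesis: Psychological health" and gives its content in one line: "Yields subscales of enhanced self-efficacy, increased community closeness, increased compassion, increased faith, lifestyle changes, enhanced family closeness, and material gain". No items, recall period or reference event are given for it. In the same section, the sleep index does have a stated one-month period.

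On timing, Section 9, Experimental Conditions, states: "Subjects will receive stool kits and a set of questionnaires to fill out at T1". Participants then "fill out the questionnaires again at T2". The Assessment visits paragraph puts the psychosocial questionnaires before the step at which participants "receive group assignment instructions at the end of the visit", so the T1 answers precede any product. The PBS is not exempted from T1.

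On analysis, Statistical Issues says that two-sample t-tests "will be used to compare change scores (post-treatment minus pretreatment) in each outcome". It adds O'Brien's test across the outcomes of each hypothesis, and a mixed model with a subject intercept, group, time and their interaction. The PBS is not exempted here either.

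**The concern.** Five of the seven subscale names describe something as having been enhanced or increased. The other two concern changes in lifestyle and material gain. A scale of this kind already asks about change, whereas most of its neighbours (affect, stress, life satisfaction) describe a state that can sensibly be subtracted across visits.

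At T1 no study product has been taken, so a perceived gain reported then must refer to something else, or to nothing in particular. Subtracting it from the T2 answer gives a score with no plain meaning for the individual. If the T1 answer is only weakly related to the T2 answer, the subtraction also adds noise. The protocol expects this pilot to inform a larger trial, so even an exploratory score should have a defined meaning.

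**Working it through.** **Inputs from the protocol.** Two-sided alpha 0.05, Cohen's d = 0.75 and 60 completers (Sample Size and Power); three groups of 20 (Section 10). The protocol does not say whether the SD behind d is that of the T2 score or of the change.

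**Assumptions.** d = 0.75 applies to the T2 score. The T1-T2 correlation r and the ratio k = SD(T1)/SD(T2) are not in the documents; r is shown as a range, and k = 1 unless stated.

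**The plan's own figure.** The stated 80% is generic, not specific to the PBS. The noncentral t gives 81.5% for 30 v 30, so the figure reproduces if the 60 completers form two groups. For 20 v 20, the pairwise comparison in this design, it gives 63.7%. That gap is a separate matter; 63.7% is the reference value below.

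**Change score.** With equal SDs, Var(change) = 2(1 - r) x Var(T2), so d_change = 0.75 / sqrt(2(1 - r)). For example, at r = 0 this is 0.75/1.414 = 0.530, and at r = 0.7 it is 0.75/sqrt(0.6) = 0.968.

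**Baseline-adjusted T2 score (ANCOVA).** Residual variance is (1 - r²) x Var(T2), so the effective d is 0.75 / sqrt(1 - r²). ANCOVA power was computed by the normal approximation only, so the change score is shown on both scales.

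Power, 20 v 20. T2 alone: 63.7% (t), 66.0% (normal).

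| r | d_change | Change, t | Change, normal | ANCOVA, normal |
|---|---|---|---|---|
| 0 | 0.530 | 37.3% | 38.9% | 66.0% |
| 0.2 | 0.593 | 44.7% | 46.6% | 67.7% |
| 0.3 | 0.634 | 49.8% | 51.8% | 70.1% |
| 0.5 | 0.750 | 63.7% | 66.0% | 78.2% |
| 0.7 | 0.968 | 84.7% | 86.5% | 91.3% |

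**When power is lost.** In general Var(change)/Var(T2) = 1 + k² - 2rk, which exceeds 1 only if r < k/2. With k = 1 the threshold is r = 0.5. With k = 0.5 it is 0.25, and power at r = 0 is 54.3%. With k = 0 (no spread at T1) there is no loss.

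**Why ANCOVA is safe at any r.** 1 - r² never exceeds 1. It also never exceeds 2(1 - r), because 1 - r² = (1 - r)(1 + r) and 1 + r is at most 2. Apart from the small cost of estimating a slope, it is at least as precise as either alternative.

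**The other planned analyses.** With both visits complete, the group x time term in a random-intercept model tests the same contrast as the change score, so the mixed model does not remove the problem. The provision to control for variables that differ between groups at baseline depends on finding an imbalance; it is not a planned baseline-adjusted analysis of T2.

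**The case against.** The strongest reply is that randomization already protects the comparison. T1 questionnaires are completed before participants receive their assignment, so the expected T1 score is the same in each arm whatever it measures. With complete follow-up, the expected difference in change then equals the expected difference at T2. This stands. A reader might infer that a difference between arms in the change score could not be read as perceived benefit, or is biased. The documents do not support that: if the T2 contrast is readable, so in expectation is the contrast in change.

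A reader might also infer that the change score necessarily loses power. That does not follow either. If T1 answers reflect something stable, such as past life experience, r could exceed 0.5 and the change score would gain. If they sit at the floor with little spread, little or nothing is lost.

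The argument also rests on subscale names, since the item wording is not in the documents, and descriptions in this section are loose: the depression inventory is described in terms of symptom change too, yet it is plainly usable at baseline. This limits confidence about the T1 answer, but does not supply the missing referent.

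Finally, it would be easy to assume that seven PBS subscales enter the psychological O'Brien composite. The examples given for that composite are affect and depressive symptoms. They are only examples, so inclusion is possible, but the protocol does not state it, nor whether subscales or a total will be analysed.

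**Conclusion.** The point holds as a minor one about interpretation and possible precision. As scheduled and analysed, the individual PBS score is a difference between two ratings of perceived gain, the first made before any product and without a stated referent. There is no bias between arms.

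The effect on power runs from a fall from 64% to 37% at r = 0, through no change at r = 0.5, to a rise to 85% at r = 0.7. This assumes 20 per arm, d = 0.75 on the T2 score and equal SDs. A low r is plausible if the two answers refer to different things, but the documents do not establish it. The PBS is one of many exploratory scales, so the microbiome and inflammation aims are not touched.

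**What to change.** Replace the change score and the group x time analysis for the PBS with a comparison of T2 scores between arms. Where the instrument allows, state the 8-week study period as its referent. There are two ways to do this:

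- Give the PBS at T2 only and compare T2 scores. This takes one line in the visit schedule and one in the analysis plan, and removes one questionnaire from T1. The downside is that there is no baseline PBS value, including for the baseline balance check.
- Keep T1 and use it as a covariate (ANCOVA). This takes one line in the analysis plan and one extra model term, and keeps the baseline value. The protocol should then also state what the T1 answer refers to.

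State whether the PBS is part of the psychological O'Brien composite. If it is, enter the T2-based statistic there.

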#### Additional Measures

Age, gender, socio-economic status, ethnic group, relationship status, education, body-mass Index and waist-hip circumference will be recorded. If for medical reasons subjects alter medications, it will be recorded via a monthly tracking form that the subject can submit.

#### **Statistical Issues**

Analytic Approach. Summary statistics (means, SDs, ranges, frequencies) will be computed for all variables of interest and compared between the treatment arms at baseline using 2-sample tests to test if randomization achieved balance in key covariates across groups. In the event of pre-existing variable group differences associated with dependent or relevant clinical variables, the nuisance variables will be statistically controlled. Outcome measures (e.g. health-related behaviors, psychological health, and objective measures of microbiome health and inflammation) will be transformed as needed to better approximate Gaussian distributions. The proposed study period is 2 months; hence we anticipate little loss-to-follow-up. However, subjects may drop out for a variety of reasons. It is important to take missing data into account when testing hypotheses of interest. Mixed-models can be applied even if some observations are missing as long as the data are "missing at random". Missing data (e.g., drop-outs) will be tested to determine if it is informative, and the methods to test for completely random dropouts will be applied. If needed, pattern-mixture models will be developed which take "missingness" into account when estimating parameters of interest using the methods of Park & Lee.

Analysis Plan. Two sample *t*-tests will be used to compare change scores (post-treatment minus pretreatment) in each outcome. Given the multiple outcomes, we will also use O'Brien's test which can be used to compare multiple endpoints across groups; we will apply O'Brien's test to the multiple outcomes for each hypothesis (e.g., psychological health via positive and negative affect, depressive symptoms; health behaviors via diet, physical activity, medication adherence, and alcohol usage). The O'Brien test statistic is a weighted linear combination of the *t*-statistics for each outcome. Finally, we will fit mixed effects models, with a subject-specific intercept included to allow for individual variability in outcome. Main covariate effects will be treatment group, time (pre-treatment and immediately post-treatment), and the group X time interaction. Likelihood ratio tests will be used to test the significance of these covariates. A significant group X time interaction will indicate that outcome trajectories differ across treatment groups.

Sample Size and Power. We hypothesized a Cohen's *d* effect-size (standardized mean difference between groups) of 0.75 based on previous studies. With at least 60 subjects completing 2 visits, we will have 80% power (2-sided alpha=0.05) to detect a 0.75 effect-size (Cohen's *d*). To be conservative, we aim to recruit 75 subjects to this study, allowing for a 20% drop-out/loss-to-follow-up rate and a total of 60 subjects completing the 2 visits. Note that our calculations did not control the Type I error for the multiple endpoints. Our objective in this small pilot study is to obtain early evidence of the putative efficacy of this novel intervention on a multitude of outcomes, psychosocial and biological, in the elderly. We expect our findings to inform the design of a larger future clinical trial in elderly subjects.

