#### **10. HUMAN SUBJECTS**

This project will recruit 75 and test a total of 60 healthy elderly subjects from UCSD ADRC. We aim to test 60 participants (20 per group, 3 groups) from UCSD.

Patients who are elderly and cognitively intact will be identified, screened, and recruited from UCSD ADRC following the procedures outlined in Section 11 below.

Study testing visits will take place at SOM Building 4.

Along with the referring physician, [name] will oversee determination of whether potential subjects fit eligibility criteria according to the criteria outlined below.

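### Adjustment covariates are picked by baseline significance tests and outcome association instead of being fixed in advance, which forgoes power and leaves the adjusted model undefined

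*Combined protocol and SAP*

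**What the plan says.** The Analytic Approach paragraph compares baseline variables between treatment arms "using 2-sample tests to test if randomization achieved balance in key covariates across groups". It then gives a two-part trigger for adjustment: "In the event of pre-existing variable group differences associated with dependent or relevant clinical variables, the nuisance variables will be statistically controlled". So a variable must differ between groups and also be associated with an outcome or a relevant clinical variable.

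The key covariates are not listed. The nearest thing to a candidate list is under Additional Measures: "Age, gender, socio-economic status, ethnic group, relationship status, education, body-mass Index and waist-hip circumference will be recorded". That sentence concerns recording, not analysis.

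The Analysis Plan paragraph names two-sample t-tests on change scores, O'Brien's test, and a random-intercept mixed model with group, time and their interaction. None contains a baseline covariate. The Randomization paragraph says the computer algorithm is meant to even out demographics across the arms, but it names neither the factors nor the method, and the analysis does not take them up.

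**The concern.** In a properly randomised trial any baseline difference is chance, so a test of it cannot show which covariates matter. The gain from adjustment comes from how strongly a covariate predicts the outcome, and this rule ignores a strong predictor that happens to be balanced. The set is chosen after the data are seen. With three arms and many outcomes, it can differ from one pair of arms to the next and from one outcome to the next.

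At stake are power that a trial with 20 per arm can ill spare, and a set of adjusted estimates that do not all answer the same question. The trial is meant to inform a larger one, so its estimates should come from a stated model. This point concerns covariates in general; use of the outcome's own T1 value is a separate matter.

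**Working it through.** **Inputs from the documents.** Effect size: "effect-size (standardized mean difference between groups) of 0.75 based on previous studies". Completers: "With at least 60 subjects completing 2 visits" and "We aim to test 60 participants (20 per group, 3 groups) from UCSD". Attrition: "allowing for a 20% drop-out/loss-to-follow-up rate", and 60/(1 − 0.20) = 75, which agrees with the recruitment target.

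**Assumptions.** Eight independent candidate covariates (the number listed under Additional Measures); 0.05 as the level for both tests; simple randomisation; correlation r of a covariate with change of 0, 0.3 or 0.5; a linear model for change as the adjusted analysis.

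**The plan's own figure.** The plan states "80% power (2-sided alpha=0.05" two-sided) at d = 0.75 with 60 completers. Power for n per arm follows from the noncentral t with noncentrality d√(n/2) and 2n − 2 degrees of freedom.
- 30 v 30: 0.75 × √15 = 2.90, power 81.5%.
- 20 v 20: 0.75 × √10 = 2.37, power 63.7%.

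The stated 80% therefore fits two arms of 30. The starting point for a comparison of two of the three planned arms is about 64%. That mismatch is a separate issue; here it only sets the baseline.

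**How often the rule triggers.** For one pair of arms, the chance of at least one baseline p < 0.05 among eight variables is 1 − 0.95^8 = 34%; over three pairs it is about 64%. The rule also needs association with the outcome. With no treatment effect and no prognostic covariate, both occur with chance 1 − (1 − 0.05 × 0.05)^8 = 2.0% (simulated 2.1%). With d = 0.75 and a pooled association test this rises to 4.6%, because an imbalanced noise variable picks up an association through the arm difference. That is the route by which bias can enter.

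**Simulation, 20 v 20, d = 0.75, 8,000 runs per setting.** Pooled means that association is tested ignoring arm; within means that it is tested within arms.

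| Prognostic covariates | Triggers, pooled / within | Mean estimate, pooled / within | Power unadjusted | Power under rule, pooled / within | Power, fixed in advance |
|---|---|---|---|---|---|
| none | 4.6% / 1.9% | 0.744 / 0.753 | 64.8% | 63.8% / 64.8% | nothing to gain |
| two at r = 0.3 | 7.7% / 5.6% | 0.738 / 0.752 | 64.1% | 62.3% / 63.8% | 70.8% |
| one at r = 0.5 | 7.9% / 6.1% | 0.739 / 0.751 | 63.5% | 62.6% / 63.9% | 75.7% |
| two at r = 0.5 | 11.4% / 10.0% | 0.740 / 0.752 | 63.6% | 63.2% / 64.5% | 88.3% |

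Separate simulations with one prognostic covariate gave 63–65% under the rule against 73–75% fixed in advance at r = 0.5, and 63–65% against 67–68% at r = 0.3. Where that covariate was the only candidate, with r = 0.5, the rule triggered in 4% of trials. It cannot exceed about 5% in that case, because a baseline p < 0.05 is required.

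**Closed-form check.** A fixed covariate divides d by √(1 − r²).
- r = 0.5: 0.75/√0.75 = 0.866. The noncentral t with 37 degrees of freedom gives 76.0%.
- r = 0.3: 0.75/√0.91 = 0.786, giving 67.8%.

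Both agree with the simulations.

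**Bias.** On the pooled reading with eight candidates, the mean falls from 0.750–0.753 unadjusted to 0.738–0.744, about 1–2%. With 20 noise candidates it falls to about 0.73, about 3%. On the within-arm reading it stays at 0.751–0.753.

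**Type I error.** Under the rule it was 4.1% to 5.3% across the null settings run.

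**Which model.** With two visits and complete data, a baseline covariate entered only as a main effect cancels out of the change. In a worked data set the group × time estimate was 0.514 with and without it, and moved to 0.429 only when covariate × time was added.

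**The case against.** The best defence is that the rule does little harm. It triggers seldom, does not inflate false positives, and costs 0–2 points of power against no adjustment. The t-tests on change contain no covariate at all, and a main effect in the mixed model would leave the group × time estimate alone. If the algorithm balances demographics as intended, imbalance on those factors is rarer than computed here. The protocol presents itself as a small pilot and is open about uncontrolled multiplicity. All of this stands. It limits the size of the problem but does not supply a covariate set or a model.

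Some stronger readings are tempting, and the documents do not support them:
- A reader might infer that the rule shrinks a true effect as a general property. That needs a pooled association test, which the plan does not specify, and even then the average effect is about 1–3%.
- In trials where the rule triggers with 20 noise candidates, the mean moves from about 0.88 unadjusted to 0.67 adjusted. This is not a bias of 0.21. The truth is 0.75, the 0.88 is itself inflated by looking only at triggered trials, and the conditional bias is 0.67 − 0.75 = −0.08.
- With 10 to 20 variables over three pairs, the chance of some imbalance is 74–93%. That counts any imbalance, not the two-part trigger.
- A fixed list does not always beat the rule. Five fixed noise covariates gave 57% power, against 60–64% under the rule.

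**Conclusion.** The point holds as a fault of pre-specification and efficiency. The plan states a data-driven way of choosing covariates, names no fixed set anywhere, and leaves the model they enter undefined. It also omits from the analysis the demographics that randomisation is meant to balance.

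The main loss is forgone power per pair of arms: about 10 points or somewhat more if one covariate correlates 0.5 with change, a few points at 0.3, and none at 0. These figures rest on assumed correlations, independent candidates, a 0.05 threshold and a linear model for change. Bias toward zero is small and depends on how association would be tested. The validity of the significance tests is not in question. This should be changed, but it does not undermine the trial.

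**What to change.** Delete the baseline significance tests and the conditional control rule, and report baseline by arm descriptively, without p-values.

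Before the code is broken, fix one short covariate list for each outcome and use it for every arm comparison of that outcome. It should hold the demographic factors used in the randomisation algorithm, which must then be named, plus at most one or two expected predictors.

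State the model: either a linear model for change with these covariates, or the mixed model with covariate × time terms. Main effects alone would leave the group × time estimate unchanged. Examine any imbalance in an unlisted variable in a labelled sensitivity analysis.

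The cost is wording, plus about one degree of freedom and a point or two of power for each listed covariate that proves non-prognostic. From the five-covariate figure, (63.7 − 57)/5 ≈ 1.3 points each. At r = 0.3 the gain is only about 4 points (67.8 − 63.7), so about three useless covariates would cancel it. The list must stay short.
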